We select a common number of clusters within each of the four study countries. The goal is to have enough clusters so that the study is powered to detect a 0.15 control group standard deviation effect (Glass’s Delta) on the Vaccine Trust Indicator (VTI), equivalent to a 7ppt. effect on the vaccination rate outcome, with 80% power and 95% confidence in an analysis that pools that data from the four countries. For the power analysis for the VTI (our primary outcome variable), we assume the control group VTI outcomes are normally distributed (we use this assumption due to the unavailability of actual distributional information on the VTI for the countries under investigation at the time of power calculation) and that all outcomes are normalized relative to the control group standard deviation. For vaccination rates, we used the most recently available (as of summer 2023) health-district-level COVID-19 vaccination rates (when available) as the input data. We simulated a 0.15 control group SD effect, which was equivalent to a 7 ppt. effect on vaccination, and then evaluated what sample size would be needed to achieve 80% power with 95% confidence. The power analysis showed that having **16 treated clusters and 16 control clusters per country and 24 households per cluster** would suffice. This implies $(16+16)*24 = 768$ **households sampled per country**, with an **overall sample size of 3,072 households and 128 clusters** across all four countries.

The study aims to increase vaccine trust, with COVID-19 vaccination being the primary basis for assessing current hesitancy. In each country, our primary focus lies on the two largest, most densely populated cities. This strategic decision is driven by the critical need for vaccination in these regions, owing to their heightened potential for disease transmission and the prevailing low COVID-19

vaccination rates. In each priority locality, clusters are defined as neighbourhoods served by health centers or clinics that meet the following criteria:

- The health center must offer COVID-19 vaccination services and services for other target vaccines (varies by country).
- For each targeted city, the health facilities used for defining the clusters must be separated by a distance of at least 4 to 5 km. This precautionary measure is taken to prevent potential spillover effects.

We proceed by describing the criteria employed for selecting priority districts within each country.

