- From whom did you receive it? (Do not read responses; add checklist: Health Ambassador, doctor, nurse, health worker, religious leader, chief or traditional leader, other relative or household member, internet/social media, books, other: specify).

[Note for Enumerator: For the control group, if the information was obtained from a friend, acquaintance, or relative who is not a family member, please provide the following details regarding the source of the information:

- A. Name of the person:
- B. Place of residence:
- C. Content of the message received regarding vaccines:

- What types of vaccinations were featured in these vaccination awareness campaigns? COVID-19, HPV, Measles, etc. [Enumerators: This is a Multiple-Choice question; kindly let the household member respond.]
- For each of the vaccine information campaigns you attended, could you please share the outreach strategy used by the organizations responsible for the campaign to make you aware of this specific type of vaccine? Billboards, Posters, Radio announcements, Door to door, Public announcements at public events, etc.
- What is the core message of each of these vaccine awareness campaigns?

Primary outcome measure

Vaccine Trust Indicator

Our primary outcome is the perceived change in vaccine confidence/receptivity following health ambassador discussions with households on vaccination trust (VTI).

The main focus is on COVID-19 or other targeted vaccine confidence, evaluated through the Vaccine Trust Index (VTI). The VTI measures confidence in the importance, safety, and efficacy of vaccines, with each item rated on a 10-point scale ranging from 1 ('strongly disagree') to 10 ('strongly agree'). We will use the 6-item VTI to assess the effectiveness of our Health Ambassador (HA) intervention, designed to enhance dialogue among adults who are vaccine-hesitant and improve trust and confidence in vaccines. The VTI, a validated tool ([Ellingson et al., 2023](#)) used in various contexts (

[Ellingson et al., 2023](#)), genuinely aids us in observing changes in trust and the shift from hesitancy to confidence. Below are the different questions to capture the Vaccine Trust Indicator.

Please give your level of agreement with each statement using the scales provided (where 1 = strongly disagree/strongly against vaccination and 10 = strongly agree/strongly in favor of vaccination).

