Please give your level of agreement with each statement using the scales provided (where 1 = strongly disagree/strongly against vaccination and 10 = strongly agree/strongly in favor of vaccination).

- 1.1. Thinking about vaccination in general, would you say you are...
1=strongly against vaccination, 10=strongly in favour of vaccination
- 1.2. I generally trust vaccine manufacturers or pharmaceutical companies
1=strongly disagree, 10=strongly agree
- 1.3. I generally trust the {country specific health department}
1=strongly disagree, 10=strongly agree
- 1.4. I understand how vaccination helps my body fight infectious disease
1=strongly disagree, 10=strongly agree
- 1.5. I feel it is important that I get vaccinated
1=strongly disagree, 10=strongly agree
- 1.6. Vaccination forms part of a healthy lifestyle
1=strongly disagree, 10=strongly agree

The items are summed to create a composite vaccine trust score. We will standardize in terms of control group standard deviations.

Secondary outcome measures

These secondary outcomes will be measured through a household questionnaire at baseline (before the intervention) and endline (after the intervention). The following questions will be asked to adult members of the household.

1. Vaccine uptake

- 1.1 For each vaccine and each target household members, the individual questionnaire will indicate whether the respondent (i) did not verbally affirm receiving the vaccination or provide documentation, (ii) verbally affirmed vaccination but did not provide documentation, or (iii) provided documentation of vaccination.

For respondents who have not been vaccinated due to time constraints or limited access to health centers, the survey will capture their intention to receive the vaccine if they were at a health center using the following question: Are you planning to be vaccinated for the [country specific disease] vaccine?

2. Knowledge about the disease: I will read you some statements and I would like you to tell me how much you agree or disagree with each statement. Please say whether you strongly agree, agree, neither agree nor disagree, disagree, or strongly disagree.
 - 2.1. [The targeted disease name] exists.
 - 2.2. I am aware of how [The targeted disease name] is transmitted.
3. To the best of my knowledge, [Targeted disease name from the list] require vaccines for their cure?
4. Vaccine/disease knowledge:

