- For each of the vaccines that have been the subject of information campaigns within the localities served by this health center in the past 3 months, what were the awareness-raising strategies employed by the respective organizations?
 - [List of vaccines with indication for type of information campaign]
- Which organization(s) led this vaccination campaign?
 - [List of vaccines with space to indicate organization(s)]
- For each of the vaccines provided at this health center, what is the vaccination rate by June 2023?
 - [List of vaccines with space to indicate rate]
- In this health/post center, have you faced any instances of vaccine shortages in the last 3 months for each of the following vaccines?
 - [List of vaccines with indication for Yes/No]

Note: For each country (Côte d'Ivoire, Malawi, Senegal, and Zimbabwe), the list of vaccines will be limited to those specifically targeted by the study. This list of vaccines varies from one country to another.

Analysis Plan

Estimating Average Effects with Household Data

For the vaccine trust and other attitudinal measures in the individual survey, we will use a hierarchical index strategy.¹ All outcome measures will first be standardized in terms of control group standard deviations. That is, we will construct a standardized sum of scores index for each of the 4 groupings listed above. Then, we will construct a global index that is a standardized sum of the grouping indices. Indexes will be oriented so that more positive values indicate a movement in the beneficial direction. For a given index, we will estimate average treatment effects using the following regression specification:

$$y_i = \alpha + \beta Treated_i + Rand. Block FE_{b[i]} + X_i' \gamma + \epsilon_i , \quad (1)$$

where i indexes the individual-survey respondent for household i , and $Rand. Block FE_{b[i]}$ and the covariate vector X_i are defined the same way as in equation (1). We calculate cluster-robust

¹ The approach follows that of Casey et al. (2012).

standard errors taking the error term ϵ_{vji} to be clustered at the level of the randomization cluster. Again, we hypothesize that $\beta > 0$, and we test using a two-sided test (allowing for the possibility that effects could go in the opposite direction as what is hypothesized) with 95% confidence. We will use a hierarchical statistical significance testing strategy:

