- For the global index, we will use the standard asymptotic p value and a two-sided null hypothesis with 95% confidence.
- If the global p-value rejects the null, then for the grouping-specific indices, we will use a Benjamini-Hochberg FDR correction for the 4 p-values.
- For any grouping index that rejects the null, we will use the Benjamini-Hochberg FDR correction for the item level p-values.

For estimating peer effects, we will use the same specification (2), with l indexing the peer respondent and $Treated_i$ indicating the treatment status of the person that recommended them.

For our behavioral outcome measured in the household roster, we will estimate the average treatment effect on the pooled vaccination rate using the following regression specification:

$$y_{vji} = \alpha + \beta Treated_i + Vaccine FE_v + Rand. Block FE_{b[i]} + X_{ji}'\gamma + \epsilon_{vji} , \quad (2)$$

where v indexes the vaccine, j indexes the individual adult in the household roster, i indexes the household, and $b[i]$ indexes the randomization block for household i . The variable $Treated_i$ is an indicator for whether the household is in a treated cluster or not. Then, $Vaccine FE_v$ are fixed effects (dummy variables) for the different vaccines and $Rand. Block FE_{b[i]}$ are fixed effects (dummy variables) for the randomization blocks. The covariate vector X_{ji} includes the following elements:

- Indicator for female of individual j ,
- Age for individual j ,
- Level of education for individual j ,
- Pre-intervention vaccination rate in the household's cluster.

We calculate cluster-robust standard errors taking the error term ϵ_{vji} to be clustered at the level of the randomization cluster. We hypothesize that $\beta > 0$, and we test using a two-sided test (allowing for the possibility that effects could go in the opposite direction as what is hypothesized) with 95% confidence. If we reject the null, we will then test effect on each individual vaccine, using the Benjamini-Hochberg FDR correction for the vaccine-level p-values.

Effect Heterogeneity with Household Data

We propose an exploratory analysis of background conditions that may moderate the size of the treatment effects on behavior and attitudes. These include:

Respondent attributes:

- Gender,
- Age,
- Level of education,
- Ethnic group (coded for collectivist norms),
- Proximity to health center.

Health ambassador attributes:

- Gender,
- Age,
- Type of degree program,

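### The primary outcome (VTI) has no ungated significance test: the written rule puts vaccine trust behind a global index and four groupings that the protocol never identifies

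*Protocol*

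**What the plan says.** **Primary outcome and sample size.** The protocol's Cluster selection section calls VTI the primary outcome variable and bases the power calculation on it: "For the power analysis for the VTI (our primary outcome variable), we assume the control group VTI outcomes are normally distributed". The target is that "the study is powered to detect a 0.15 control group standard deviation effect", "with 80% power and 95% confidence in an analysis that pools that data from the four countries". Under Primary outcome measure, VTI is a six-item score: "The items are summed to create a composite vaccine trust score". It is then standardized to the control-group SD.

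**Testing rule.** Under Analysis Plan, Estimating Average Effects with Household Data, vaccine trust and the other attitudinal measures go together into one hierarchical index strategy: "That is, we will construct a standardized sum of scores index for each of the 4 groupings listed above". A global index is then formed from the grouping indices. Each index is analysed with model (1). On sidedness and level, the section states: "we test using a two-sided test (allowing for the possibility that effects could go in the opposite direction as what is hypothesized) with 95% confidence".

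The order is:
1. The global index is tested at two-sided 5%.
2. "If the global p-value rejects the null, then for the grouping-specific indices, we will use a Benjamini-Hochberg FDR correction for the 4 p-values".
3. Items are tested, with a further Benjamini-Hochberg (BH) correction, within any grouping that rejects.

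Pooled vaccination uptake is analysed separately with model (2), at its own two-sided 5%.

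**The concern.** The sample size section and the analysis section describe different trials. The first assumes one test of one score. The second has no such test: significance for anything in the vaccine-trust family is reached through a composite that also holds knowledge, belief, access and healthcare-trust measures.

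The rule is also not fully defined. It refers back to a list of four groupings, and no list of four exists. The analyst would have to decide which headings to merge and whether VTI stands as a grouping. Both choices affect whether the trial's main claim can be made, and they could be made after endline data are seen.

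**Working it through.** **1. Look for the four groupings.** The outcome sections list VTI as primary, then eight numbered secondary headings: uptake; disease knowledge; a one-question item on vaccines and cure; vaccine/disease knowledge; beliefs; access; vaccine confidence; trust in the healthcare system. Uptake has its own model, which leaves VTI plus seven attitudinal headings. Four groupings arise only through a merger that is not stated.

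Two readings follow:
- *VTI is not one of the four groupings.* No significance test of the VTI score is then specified. Model (1) can still give an effect estimate.
- *VTI is one of the four.* It is declared only if the global test rejects and VTI also passes BH over four p-values.

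**2. Try to reproduce the 80%.** Inputs from the protocol: 3,072 households, 128 clusters, 24 per cluster, 1:1 allocation, effect 0.15 SD, two-sided 5%. With intracluster correlation (ICC) ρ, the design effect is DE = 1 + 23ρ and the expected z is 0.15 × √(3072 / (4 × DE)).
- With ρ = 0: z = 0.15 × √768 = 4.157, power 98.6%.
- 80% power needs z = 1.960 + 0.842 = 2.802, so DE = (4.157/2.802)² = 2.20 and ρ = 1.20/23 = 0.052.
- Power by assumed ICC: 93.1% at 0.02, 80.9% at 0.05, 62.9% at 0.10.

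The protocol gives no ICC, so the 80% is not verifiable. It is taken as given below, with expected z = 2.802 for VTI.

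**3. Direction of the effect, under the second reading.** The BH threshold for any one grouping is at most 0.05, and the global test must reject as well. Power to declare VTI therefore cannot exceed its stand-alone power. This needs no assumption about correlations or other effects.

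**4. Size of the effect.** Assumptions: four groupings, VTI effect 0.15 SD, a common correlation r between the grouping z statistics, and a common effect on the other three. The global statistic is the sum of the four z values divided by √(4 + 12r). At r = 0.3 the divisor is √7.6 = 2.757.

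| Effect on the other three | Expected global z | Global test rejects | VTI declared (global test and BH) |
|---|---|---|---|
| 0.15 SD | 4 × 2.802 / 2.757 = 4.07 | 98% | 76% |
| 0.10 SD | 3 × 2.802 / 2.757 = 3.05 | 86% | 67% |
| 0.05 SD | 2 × 2.802 / 2.757 = 2.03 | 53% | 46% |
| 0 | 2.802 / 2.757 = 1.02 | 17% | 17% |

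The last column comes from 400,000 simulated draws per row; stand-alone VTI power in the same draws is 80%.

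**5. Sensitivity.**
- Over r = 0.1 to 0.7, the all-equal case runs from 77% to 75% and the VTI-only case from 21% to 12%.
- At r = 0.3 with one of the other three groupings null and two at 0.15 SD, power is 70%; with two null it is 48%.
- With the 3,773 baseline households of Table A1 before attrition (ICC 0.052, r = 0.5), stand-alone power is 83%. Gated power is 79.5% if all move equally, 58% if the others move half as much, and 15% if only VTI moves.

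**The case against.** **The loss may be small.** The secondary blocks overlap with VTI in content: beliefs about safety and necessity, vaccine confidence, confidence in the government healthcare system. The protocol's section on mechanisms also expects access, awareness and trust in the medical system to change. On that theory the groupings move together and the loss is about 4 points at r = 0.3. This stands, and it makes the 17% figure a worst case rather than an expectation.

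**The 80% may still be reached.** A reader might infer that the trial fails to deliver 80% power for VTI. The documents do not support that as a flat statement, because no ICC is given. At an assumed ICC of 0.02 and r = 0.3, gated power would be 92% if all groupings move 0.15 SD, though only 24% if VTI alone moves.

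**A VTI effect is not blocked outright.** A reader might also infer that a real VTI effect could not be declared if knowledge or access did not respond. That is too strong: the 70% and 48% results above show reduced power, not impossibility.

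**The method is legitimate in itself.** A global-index gate suits many outcomes of equal standing. The difficulty is its use where one outcome was named primary and powered alone. The separate 5% test for uptake is likewise defensible, since uptake is a secondary behavioural family with its own BH step; it is not an error.

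**A SAP may fill the gap.** It could name the groupings. It would not cure the wrong cross-reference, and an ungated VTI test there would depart from the order that the protocol fixes.

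**Conclusion.** The point holds as an internal contradiction. The protocol powers one test and prescribes another, and the prescribed one depends on four groupings that it does not identify.

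Three things follow from the text alone: there is no ungated VTI test; the groupings match no list; and, if VTI is a grouping, its power under the written rule is no higher than when tested alone. The size of the loss rests on assumptions. With stand-alone power of 80% and r = 0.3, it runs from about 4 points (all groupings move equally) to about 63 points (only VTI moves). If VTI is not a grouping, these figures do not apply, and the defect is that the primary outcome has no testing rule.

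This should be corrected before endline data are examined, because it governs the trial's main claim.

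**What to change.** In Estimating Average Effects with Household Data:
1. State that the primary confirmatory test is the standardized VTI score in model (1), two-sided 5%, not conditional on the global index.
2. Replace the reference to groupings listed above with a named list of four, saying which numbered headings each contains. The choice of merger is the investigators', but it must be written down.
3. Apply the global index and both BH steps to those secondary attitudinal groupings, without VTI.

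Pooled uptake can stay as a separate secondary family. Placing it, or the secondary index, in a fixed order behind VTI is optional.

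The cost is wording only, with no change to sample, fieldwork or questionnaire. The downside is that the global index no longer includes VTI, so it becomes a summary of secondary attitudes only. The restored test has the stated 80% power if the unstated ICC is about 0.052; the ICC used in the power calculation should be added so that this can be checked.

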The randomized controlled trial operate as a multisite locality-level cluster-randomized experiment across Côte d'Ivoire, Malawi, Senegal, and Zimbabwe. The treatment is whether a locality received "health ambassadors" in combination with any already-existing public outreach (treated = 1) versus no additional intervention above and beyond any already-existing public outreach (control = 0). We randomly assign half of the clusters to treatment and the other half to control. The randomization is stratified on the basis of city, and where possible, health district within city. The result will be a balanced block-cluster random assignment of 16 clusters to treatment and 16 clusters to control per country, for a total of 64 treated clusters and 64 control clusters. The statistical analysis will control for the block stratification.

Household Recruitment

Household Recruitment

We define households using the definition from the international Demographic and Health Surveys (eat from the same pot, live under the same roof, and share the same household head). In selected clusters, after obtaining approval from health district authorities to proceed with field activities, field enumeration staff (*separate from the health ambassadors*) will operate under the research team's supervision to employ the following process to identify the households to be surveyed in the cluster. As explained above, our target is 24 households per cluster. However, since the study is conducted in densely populated urban areas where households may migrate, field enumerators were instructed to survey 30 households per cluster to account for potential attrition. Due to logistical challenges, such as difficulties in finding eligible households during the survey period and data quality control measures that prompted some enumerators to survey more than 30 eligible households, cluster sizes ended up varying between 24 (in Zimbabwe) and 37 (in Côte d'Ivoire). Table A1 presents the total number of households and adults surveyed at baseline by country.

1. Using Google Maps, we map the outline of each cluster and geolocate the focal health facility where free vaccination is available for all of the target vaccines in the country.
2. We stratify the area into 5 or 6 bands of increasing distance from the health facility.
3. We randomly sample a geolocated point within each band.
4. Using Google Maps, we identify the home nearest to each of those sampled points.

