5. We choose the home nearest to the sampled point.
6. On the same side of the street as that first home, demarcate a total of 6 additional homes that are evenly between the first selected home and either end of the street.
7. Randomly order these 6 additional homes and select the first three.
8. If a home includes more than one household, we number them and then draw one number at random from a hat.
9. If a household either does not consent to participation in an initial intake, is ineligible (see below), or does not consent to participate in the full study, then move to the next household in the list of 6. If one exhausts this list, then perform the same enumeration strategy on the other side of the street.

Upon being selected, an enumerator approach the household head or adult representing the household for their consent for a brief intake survey to determine the household's eligibility. Households will be eligible if it contains at least one adult member who was eligible for COVID vaccination but has never been vaccinated against COVID-19.

If eligible, the household head or adult representing the household will be asked for their consent to participate in the full study, which would involve being approached at a future date for in person "discussions of health-related issues, including adult vaccination." This consent process will be done for households in both treated and control clusters. For those in treated clusters, such "discussion" would include the visit from the health ambassador and then the endline survey. In control clusters, such "discussion" would include only the endline survey.

Recruitment and Mobilization of Health Ambassadors

Profile

The intervention aims to mobilize Health Ambassadors who meet the following criteria:

- Willing to work on a volunteer basis, exhibiting intrinsic motivation to contribute to social welfare and a willingness to engage households in an empathetic manner;
- Up to date on vaccination for COVID and other target diseases;
- Possess enough education and capacity to be a “voice for science”, that is, to effectively and accurately communicate the scientific processes and regulations that ensure vaccine safety, the scientifically understood protective benefits of vaccines, and the scientifically understood risks of vaccinations; and
- Possess connections to the communities in which target households reside so as to operate on the basis of trust.

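### The model for the attitude outcomes adjusts for no respondent-level baseline outcome, which forgoes precision; its covariate reference and the wording of the primary outcome also need repair.

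*Protocol*

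**What the plan says.** **Covariates.** In the Analysis Plan (Estimating Average Effects with Household Data), model (1) regresses an attitude index on treatment, randomization-block effects and a covariate vector. That vector is said to be defined as in equation (1), which is the model itself. The only list stands under equation (2), the roster vaccination model. It holds sex, age, education and a last entry that starts "Pre-intervention vaccination rate in the household" and refers to the household's cluster.

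**Baseline data.** Under Secondary outcome measures: "These secondary outcomes will be measured through a household questionnaire at baseline (before the intervention) and endline (after the intervention". Appendix Table A1 counts 3,773 households and 12,618 adults surveyed at baseline. No sentence says outright that the VTI was asked at baseline, although the VTI is said to be a tool that "genuinely aids us in observing changes in trust and the shift from hesitancy to confidence".

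**Primary outcome.** It is introduced as the "perceived change in vaccine confidence/receptivity following health ambassador discussions with households on vaccination trust (VTI". A little further on, the score is built differently: "The items are summed to create a composite vaccine trust score", expressed in control-group standard deviations. Control clusters receive "no additional intervention above and beyond any already-existing public outreach (control = 0". For their households, the discussion announced at consent "would include only the endline survey".

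**The concern.** An attitude measured on the same household before the intervention would be expected to predict the endline attitude better than sex, age, education and a cluster vaccination rate do. If it is collected and left out, the effect estimate has a larger standard error than it needs. Chance differences in starting trust between the 64 treated and 64 control clusters then stay in the estimate as noise.

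The introductory sentence on the primary outcome adds a second difficulty. It speaks of change after ambassador visits, while model (1) is written for a score with no baseline term. An endline level, a raw change and a baseline-adjusted level have different variances, so the protocol should say which one is meant before the outcome data are analysed.

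**Working it through.** **Inputs from the protocol (Cluster selection; Analysis Plan).** Effect 0.15 control-group SD, 80% power, two-sided 5% level, 16 + 16 clusters in each of four countries, 24 households per cluster.

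**Inputs assumed, because the protocol gives none.** The ICC, the baseline-endline correlation r, and 118 degrees of freedom for a t test on cluster-level variation. A normal approximation moves the power figures by less than one percentage point.

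**1. The plan's own figures.** (16 + 16) × 24 = 768 per country, and 768 × 4 = 3,072 households in 128 clusters. Both reproduce. The 80% power came from a simulation whose ICC is not stated, so it can be matched only by solving for one:
- without clustering, n per arm = 2 × ((1.96 + 0.84)/0.15)² ≈ 698
- available per arm: 64 × 24 = 1,536, so the design effect allowed is 1,536/698 = 2.20
- implied ICC = (2.20 − 1)/(24 − 1) ≈ 0.052

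Below, ICC = 0.05 is used.

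**2. Without a baseline score.** SE = √[(4/128) × (0.05 + 0.95/24)] = √(0.03125 × 0.0896) = 0.0529. Power is 80%, and the detectable effect is 2.8 × 0.0529 = 0.148 SD.

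**3. With a baseline score.** Two cases bracket the gain:
- r holds at both levels: variance term (1 − r²) × (0.05 + 0.95/24)
- only household-level variance is explained: variance term 0.05 + 0.95 × (1 − r²)/24

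| r | Variance cut, both levels | Power | Detectable effect (SD) | Variance cut, household only | Power | Detectable effect (SD) |
|---|---|---|---|---|---|---|
| 0.3 | 9% | 84% | 0.141 | 4% | 82% | 0.145 |
| 0.5 | 25% | 90% | 0.128 | 11% | 85% | 0.140 |
| 0.7 | 49% | 98% | 0.106 | 22% | 89% | 0.131 |

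**4. Sensitivity to the ICC.** At ICC 0.10, power without baseline is 62%. It becomes 66 / 75 / 89% (both levels) or 63 / 65 / 68% (household only). At ICC 0.02 it starts at 93% and becomes 95 / 98 / over 99%, or 94 / 96 / 99%.

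**5. Level, change and adjusted level.** With equal variances at both times, relative to an endline-only variance of 1, a raw change score has variance 2(1 − r) = 1.4 / 1.0 / 0.6 and baseline adjustment has 1 − r² = 0.91 / 0.75 / 0.51. At r = 0.3, a change score would be less precise than ignoring the baseline. The choice of analysis therefore matters.

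**The case against.** The best case for leaving the plan alone runs as follows.

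- **This is a matter of efficiency.** That stands. A reader might infer that omitting the baseline biases the result or invalidates the comparison. It does neither: under randomisation the endline contrast estimates the same effect as a change contrast, and the cluster-robust standard error already reflects chance imbalance. Nor does the sample-size section claim any baseline adjustment, so the stated power does not depend on one.
- **A baseline VTI is not established.** That stands too. A reader might infer from Table A1 that starting trust is on file for all 3,773 households. The table counts households surveyed, not attitude items completed, and the baseline-and-endline sentence covers the secondary outcomes. For those outcomes the point holds directly; for the VTI it depends on what was asked. A substitute built from other items would probably have a lower r.
- **The gain may be small.** It may. If the baseline explains household-level variance only and r is 0.3, the gain is about two percentage points. Block effects and the cluster vaccination rate may already take up some of the cluster-level part. The individual questionnaire goes to the head or, if unavailable, another adult, so the two respondents may differ, which lowers r.
- **The outcome wording is only drafting.** Largely so. A reader might infer that the primary outcome does not exist in half the trial. The six-item sum can be scored in both arms, and the protocol promises the same measurement in both. The introductory sentence is still wrong as it stands.
- **The analysis plan may settle it.** The protocol does not leave the covariates open. It lists them, and the reference in model (1) fails on its own terms.

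**Conclusion.** The point holds as a forgone gain in precision together with two repairs to the text. No respondent-level baseline outcome appears in the only covariate list, while baseline collection is stated for the secondary attitude measures. At ICC 0.05 and r between 0.3 and 0.7, adjustment would lift power from 80% to between 82% and 98%. The lower end applies if r is 0.3 and only household-level variance is explained, the upper end if r is 0.7 at both levels. Both the ICC and r are assumptions, and a different baseline instrument or respondent would reduce the gain. For the VTI, on which the trial was sized, the gain is conditional on a usable baseline measure. The change should be made, but the trial's validity does not depend on it.

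**What to change.** 1. State whether the six VTI items were asked at baseline.
2. Add to the covariates of model (1) the baseline value of the same score or index, for every attitude outcome measured at baseline. For the VTI, use its baseline score if collected, otherwise the baseline index of secondary-outcome blocks 5 (beliefs) and 7 (vaccine confidence).
3. Set missing baselines to the mean and add a missingness indicator, so that no household is dropped for lack of a baseline.
4. Prespecify a rule for a baseline given by a different household member, for example keeping it as the household's baseline with a mismatch indicator. Who answers at endline is settled after randomisation, so report mismatch by arm and repeat the analysis without that indicator.
5. Correct the reference in model (1) so that its covariates are the list under equation (2) plus the baseline outcome.
6. Define the primary outcome as the endline six-item VTI score compared between arms, and remove the wording on perceived change after ambassador discussions.

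The cost is a few sentences and some data handling to match respondents and flag missing baselines. No new data are needed. The changes should be fixed before outcome data are analysed, so that the choice among level, change and adjusted level is not open afterwards.
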